10.4.3 Pharmacokinetic Analyses

Serum concentration data will be listed and summarized by time point for each dose level using descriptive statistics (number of subjects, mean, SD, coefficient of variation [CV], minimum, median, and maximum). Serum concentration versus time profiles for each subject will be presented graphically. The mean serum concentrations versus scheduled time profiles will be presented graphically by dose.

The PK parameters of AV-1 will be analyzed based on the actual sampling times. All parameters will be calculated using the latest version of Phoenix[®] WinNonlin[®] (Certara USA Inc., Princeton, New Jersey) or SAS[®] (SAS Institute Inc., Cary, North Carolina). Pharmacokinetic parameters will be summarized by time point for each dose level using descriptive statistics (number of subjects, arithmetic mean, SD, CV, minimum, median, and maximum). Geometric means and geometric CV will be reported for AUC₀-tlast, AUC₀-∞, and C_{max}. The following serum PK parameters will be calculated as data permit:

C_{max}	Maximum observed serum concentration
T_{max}	Time to reach maximum observed serum concentration
AUC ₀₋₄₈	Area under the serum concentration-time curve from time 0 to 48 hours postdose, calculated using the linear trapezoidal rule method
AUC _{0-tlast}	Area under the serum concentration-time curve from time 0 to the last quantifiable concentration, calculated using the linear trapezoidal method
AUC₀-∞	Area under the serum concentration-time curve from time 0 extrapolated to infinity, calculated as [AUC _{0-tlast} + (C _t / λ_z)] where C _t is the last observed serum drug concentration. %AUC _{exp} must be <0.20 to retain AUC _{0-∞} in the summary and statistical tables
t _{1/2}	Apparent terminal half-life, calculated as $ln(2)/\lambda_z$
CL	Total serum clearance, calculated as Dose/AUC₀-∞
V_z	Volume of distribution during the terminal phase, calculated as Dose/AUC $_{0\infty}$ * λ_z

In addition to the above PK parameters, which will be listed and summarized, the following parameters will also be listed to document the selection of data points used to estimate t_{1/2} using noncompartmental procedures:

%AUC _{exp}	Percentage of the area extrapolated for calculation of $AUC_{0-\infty}$
λ_z	Apparent terminal elimination rate constant
Number of points	Number of data points used to estimate λ_z ; a minimum of 3 data points must be used, and C_{max} must not be included
λ_z lower (h)	Lower bound used for the estimation of λ_z

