- (l) Clinical laboratory testing will occur at Screening, Check-in, predose (within 60 minutes) and 48 hours after the start of the IP infusion on Day 1; and on Days 8, 15, 22, 43, 85, and 120. A complete list of assessments is provided in Section 7.2. Blood and urine samples will be collected under fasted conditions and prepared per the clinic's standard procedures.
- (m) Urine drug screen will occur at Screening and Check-in and on Days 22, 43, and 85 per the clinic's standard procedures and per Section 7.2.

- (n) Women of childbearing potential only. A serum pregnancy test will be performed at Screening and Check-in, and tests must be negative prior to enrollment and dosing, respectively.
- (o) After verification of eligibility, subjects will be randomly assigned before dosing on Day 1.
- (p) The start of the IP infusion will be called "0" hour and is denoted with grey shading. All doses of the IP will be administered intravenously over a period of 60 minutes. Subjects will maintain an upright (ie, seated or standing) position for at least 4 hours after the end of infusion.
- ^(q) Blood samples for PK analysis of AV-1 in serum will be collected predose (within 15 minutes); at 0.5, 1 (end of infusion), 1.25, 1.5, 2, 3, 4, 6, 8, 12, 24, and 48 hours after the start of infusion, Day 5 prior to discharge, and at the follow-up visits on Days 8, 15, 22, 29, 43, 57, 85, and 120 (or ET).
- A blood sample will be drawn on Day –1 and tested only if a suspected hypersensitivity reaction occurs during or following infusion on Day 1 at the discretion of the Investigator in consultation with the Sponsor. At the discretion of the Investigator, an additional blood sample will be drawn as soon as possible after the event occurs (Day 1) and again the following day (Day 2).
- (s) During fasting periods, subjects should have nothing to eat or drink except water from 10 hours prior to start of the IP infusion until 4 hours after the end of infusion.
- (t) During non-fasting periods when subjects are at the clinical site, subjects should receive standardized meals per the clinic's standard procedures that are scheduled at the same time in each treatment period during the study.

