8.3. Serum Pharmacokinetic Parameters

The serum concentration-time data for AV-1 will be analyzed by non-compartmental analysis using Phoenix[®] WinNonlin[®] (Certara USA, Inc., Princeton, NJ) Version 8.0 or higher. Actual sampling times will be used for the estimation of all serum PK parameters.

PK parameters of AV-1 will be summarized using descriptive statistics by dose group. If data allow, the following PK parameters will be calculated:

Parameter	Description
C _{max}	Maximum observed serum drug concentration
T _{max}	Time to reach maximum observed serum concentration
AUC ₀₋₄₈	Area under the serum concentration-time curve from time 0 to 48 hours
	postdose, calculated using the linear trapezoidal method
AUC _{0-tlast}	Area under the curve from time 0 to the last quantifiable concentration,
	calculated using the linear trapezoidal method
AUC _{0-∞}	Area under the serum concentration-time curve from time 0 extrapolated
	to infinity, calculated as $[AUC_{0-tlast} + (C_t/\lambda_z)]$ where C_t is the last
	observed serum drug concentration. %AUCexp must be <0.20 to retain
	$AUC_{0-\infty}$ and associated parameters in the summary and statistical tables
t1/2	Apparent terminal half-life, calculated as: $\ln(2)/\lambda_z$
CL	Total serum clearance, calculated as Dose/AUC _{0-∞}
Vz	Volume of distribution during the terminal phase, calculated as
	$Dose/AUC_{0-\infty}$ * λ_z

In addition to the above PK parameters, which will be listed and summarized, the following parameters will also be listed to document the selection of data points used to estimate $t_{1/2}$ using non-compartmental procedures:

Parameter	Description
%AUC _{exp}	Percentage of the area extrapolated for calculation of $AUC_{0-\infty}$.
λ_z	Apparent terminal elimination rate constant, where λ_z is the magnitude of the slope of the linear regression of the log concentration versus time profile during the terminal phase.
Number of points	Number of data points used to estimate λ_z ; a minimum of 3 data points must be used, and C_{max} must not be included.
λ_z lower	Lower bound used for the estimation of λ_z .
λ_z upper	Upper bound used for the estimation of λ_z .
Rsq	r^2 , the coefficient of determination (goodness of fit statistic); visual inspection of the terminal slope will be performed. In general, λ_z may only be retained if $r^2 \ge 0.80$

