10.5. Physical Examination

A full physical examination will be performed at Screening (skin, head, ears, eyes, nose, throat, neck, thyroid, lungs, heart, cardiovascular, abdomen, lymph nodes, and musculoskeletal system/extremities). Focused examination (lungs, cardiovascular, abdomen, and skin) will be performed on Days 5, 8, and 15. Targeted, symptom-directed physical examinations will be performed at all other follow-up visits. Physical examination results will be presented in a data listing for the safety population.

11. Changes from the Planned Analysis

Different from the Protocol, the safety population is defined as all subjects who receive any amount of IP in this SAP.

12. Interim Analysis

No formal interim analysis is anticipated for this study. The blinded safety data will be reviewed by the investigators, Medical Monitor and Sponsor's representative to ensure that it is safe to proceed with the planned dose escalation of IP.

13. References

International Council for Harmonisation (ICH) E6 (R2) GCP: Integrated Addendum to ICH E6 (R1) Guidance for Industry, published in the Federal Register (83 Federal Register 8882 [2018]) https://www.fda.gov/media/93884/download.

mups.//www.iua.gov/mcuia/95884/uowmoau.

Protocol AV1-PPD-0005: A Phase 1a, Double-Blind, Placebo-Controlled, Single Ascending Dose Study to Determine the Safety and Pharmacokinetics of AV-1 in Healthy Male and Female Adult Subjects, Protocol Amendment 2, 07 May 2020.

14. Appendices

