Appendix 1 Schedule of Events

Phase Screening Check-ir				Treatment Period										EOS/ ET	
Procedure ^(a)	Day	-35 to -2	-1	1	2	3	5	8 (+2)	15 (±2)	22 (±2)	29 (±2)	43 (±3)	57 (±3)	85 (±5)	120 (±5)
Admission to clinic			Х												
Discharge from clinic ^(b)							X								
Outpatient visit								X	Х	X	Х	X	Х	X	X(c)
Informed consent		Х													
Demographics		X													
Serology ^(d)		X													
Flavivirus serology test(e)		X													
Serum FSH ^(f)		Х													
Inclusion/exclusion criteria		Х	Х												
Medical history ^(g)		X	Х				X	Х	Х	Х	Х	X	Х	X	Х
Height, weight, and BMI ^(h)		X	Х											X	Х
Physical examination ⁽ⁱ⁾		X	Х				X	Х	Х	Х	Х	X	Х	X	Х
Vital sign measurements ^(j)		X	Х	Х	X	Х	X	Х	Х	Х		X		X	Х
12-lead ECG ^(k)		X		Х	X			Х				X		X	Х
Clinical laboratory testing ^(I)		X	Х	Х		X		Х	X	X		X		X	Х
Urine drug ^(m)		Х	Х							X		X		X	
Urine cotinine testing			Х												
Pregnancy test ⁽ⁿ⁾		Х	Х												
Randomization ^(o)				Х											
AV-1 or placebo administration ^(p)				Х											
PK blood sample collection ^(q)				Х	X	X	X	X	X	X	X	X	X	X	Х
Anti-AV-1 antibody blood sample			v								v			v	v
collection			л								А			л	л
Hypersensitivity panel collection ^(r)			Х	Х	X										
Fasting period ^(s)			Х	Х											
Non-fasting period ^(t)					X	X	X								

DLass		Treatment Period										EOS/		
Phase	Screening	Cneck-in			-									EI
							8	15	22	29	43	57	85	120
Procedure ^(a) Day	-35 to -2	-1	1	2	3	5	(+2)	(±2)	(±2)	(±2)	(±3)	(±3)	(±5)	(±5)
Solicited AEs, Unsolicited AEs, and									v.					,
SAEs ^(u)			•											
Prior/concomitant medications		↓						- X						•

Abbreviations: AEs, adverse events; BMI, body mass index; ECG, electrocardiogram; EOS, end of study, ET, early termination; FSH, folliclestimulating hormone; IP, investigational product; PK, pharmacokinetic; QTcF, QT interval corrected for heart rate using Fridericia's formula; SAE, serious adverse event.

Notes:

- (a) When procedures overlap or occur at the same time point, they should be performed in the following order: ECG, vital signs, then PK sampling which should be timed to occur last and as close to the scheduled time window as possible.
- ^(b) Discharge from the clinical site on Day 5 after all study related activities are completed.
- ^(c) The final follow-up visit will occur on Day 120 (approximately Week 17).

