- (1) Clinical laboratory testing will occur at Screening, Check-in, predose (within 60 minutes) and 48 hours after the start of the IP infusion on Day 1; and on Days 8, 15, 22, 43, 85, and 120. A complete list of assessments is provided in protocol Section 7.2 Blood and urine samples will be collected under fasted conditions and prepared per the clinic's standard procedures.
- ^(m) Urine drug screen will occur at Screening and Check-in and on Days 22, 43, and 85 per the clinic's standard procedures and per Section 7.2.
- ⁽ⁿ⁾ Women of childbearing potential only. A serum pregnancy test will be performed at Screening and Check-in, and tests must be negative prior to enrollment and dosing, respectively.
- ^(o) After verification of eligibility, subjects will be randomly assigned before dosing on Day 1.
- (p) The start of the IP infusion will be called "0" hour and is denoted with grey shading. All doses of the IP will be administered intravenously over a period of 60 minutes. Subjects will maintain an upright (ie, seated or standing) position for at least 4 hours after the end of infusion.
- ^(q) Blood samples for PK analysis of AV-1 in serum will be collected predose (within 15 minutes); at 0.5, 1 (end of infusion), 1.25, 1.5, 2, 3, 4, 6, 8, 12, 24, and 48 hours after the start of infusion, Day 5 prior to discharge, and at the follow-up visits on Days 8, 15, 22, 29, 85, and 120 (or ET).
- (r) A blood sample will be drawn on Day -1 and tested only if a suspected hypersensitivity reaction occurs during or following infusion on Day 1 at the discretion of the Investigator in consultation with the Sponsor. At the discretion of the Investigator, an additional blood sample will be drawn as soon as possible after the event occurs (Day 1) and again the following day (Day 2).
- ^(s) During fasting periods, subjects should have nothing to eat or drink except water from 10 hours prior to start of the IP infusion until 4 hours after the end of infusion. Water is permitted as desired except for the period of 1 hour prior to the start of the IP infusion until 1 hour after the end of the infusion.
- ^(t) During non-fasting periods when subjects are at the clinical site, subjects should receive standardized meals per the clinic's standard procedures that are scheduled at the same time in each treatment period during the study.

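### The AUC0-inf retention cut-off of 0.20 is applied to a parameter defined as a percentage, so as written it means 0.2%; the SAP's PK sampling lists also omit Days 43 and 57

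*SAP*

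**What the plan says.** **Cut-off.** SAP 8.3 describes %AUCexp as "Percentage of the area extrapolated for calculation of" AUC0-inf, and in the same section sets the rule "AUCexp must be <0.20 to retain" AUC0-inf. Protocol 10.4.3 gives the same definition and the same limit, "must be <0.20 to retain". Neither attaches a percent sign to 0.20 or says that a fraction is meant.

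**Scope.** In the protocol the rule covers AUC0-inf alone. The SAP adds "and associated parameters in the summary and statistical tables", with no list of what is associated. SAP Section 11 records one departure from the protocol: "Different from the Protocol, the safety population is defined as all subjects who receive any amount of IP in this SAP".

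**Sampling days.** Footnote q of SAP Appendix 1 places the late PK samples "at the follow-up visits on Days 8, 15, 22, 29, 85, and 120 (or ET", and SAP 8.2 has the same days. Footnote q of the protocol schedule has "at the follow-up visits on Days 8, 15, 22, 29, 43, 57, 85, and 120 (or ET", and protocol 3.1 and 7.2.2 agree with it. The row "PK blood sample collection" in the SAP's own grid is marked at every visit from Day 1, including Days 43 and 57.

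**The concern.** A retention rule decides which subjects enter a summary, so its unit has to be fixed before concentrations are seen. A programmer who computes %AUCexp as defined and applies the limit as printed discards every AUC0-inf with 0.2% or more extrapolated. PK is a secondary objective, and AUC0-inf, CL and Vz are named secondary endpoints. AUC0-inf also supplies one of the three dose-proportionality fits in SAP 8.4.

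Leaving the associated parameters unnamed adds a second uncertainty. CL and Vz contain AUC0-inf in their formulas and can be inferred. Half-life depends only on λz, which has its own r² criterion, so two programmers could summarise t1/2 on different subjects.

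The short sampling lists matter mainly for the concentration summaries, which follow the planned times, and for the mean plot by nominal time. Built from those lists, both would show nothing between Day 29 and Day 85.

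**Working it through.** The cut-off is a stated rule, not a derived figure, so there is no plan calculation to reproduce. The check is what each reading would do.

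**Inputs from the documents:** last PK visit Day 120 (±5), that is T = 119 days after dosing (114 to 124); 6 × 5 = 30 AV-1 subjects; 1-hour infusion; linear trapezoids; the nominal sampling times.

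**Assumptions:** half-life (the study is first-in-human and no value is given), its between-subject CV, curve shape, and concentrations quantifiable to the last visit.

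**Step 1: what each reading requires.** For a mono-exponential decline the extrapolated share is 2^(−T/t½).

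- 0.2%: a fall of 1/0.002 = 500-fold, or log2(500) = 8.97 half-lives. Largest t½ = 119/8.97 = 13.3 days (12.7 to 13.8 over the visit window).
- 20%: a fall of 1/0.20 = 5-fold, or log2(5) = 2.32 half-lives. Largest t½ = 119/2.32 = 51 days (49 to 53).

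A noise-free non-compartmental calculation on the planned times, with λz from the last three points, agrees. The bi-exponential curve assumes a 50% fast phase with a 1.5-day half-life.

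| Half-life (days) | %AUCexp, mono-exponential | %AUCexp, bi-exponential |
|---|---|---|
| 13 | 0.17 | 0.15 |
| 14 | 0.27 | 0.24 |
| 21 | 1.94 | 1.80 |
| 28 | 5.19 | 4.91 |
| 50 | 19.1 | 18.5 |
| 60 | 25.2 | 24.6 |

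Between about 14 and 50 days, AUC0-inf is dropped on one reading and kept on the other.

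**Step 2: how many subjects stay.** Retained share = P(t½ < threshold), with t½ lognormal. Example: median 12 days, CV 25%, so σ = √ln(1 + 0.25²) = 0.246; z = ln(13.3/12)/0.246 ≈ 0.41; share ≈ 0.66, about 20 of 30.

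| Assumed median t½ (days) | Kept at 0.2%, CV 25% | Kept at 0.2%, CV 15 to 30% |
|---|---|---|
| 7 | 30 of 30 | 98–100% |
| 10 | 26 | 83–97% |
| 12 | 20 | 63–75% |
| 14 | 12 | 36–43% |
| 21 | 1 | 0–6% |
| 28 | 0 | 0–1% |

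The 20% reading keeps 98 to 100% throughout.

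**Step 3: Days 43 and 57, if those samples were really left out of the AUC.** Example with t½ = 14 days and starting concentration 1. The values at 28, 42, 56 and 84 days after dosing are 0.25, 0.125, 0.0625 and 0.0156.

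- One trapezoid from 28 to 84 days: 56 × (0.25 + 0.0156)/2 = 7.44.
- Three trapezoids with the two samples: 2.63 + 1.31 + 1.09 = 5.03.
- Exact area to 119 days: (14/ln 2) × (1 − 2^(−8.5)) = 20.14.
- Added error: (7.44 − 5.03)/20.14 ≈ 12%.

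The full calculation gives an overstatement of AUC0-tlast at 14 days of 14.2% without the two samples and 2.3% with them. Over half-lives of 7 to 28 days and both curve shapes, the ranges are 6.7 to 15.5% without and 1.4 to 3.8% with.

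**The case against.** **20% is the obvious intent.** The r² criterion in the same section is also a decimal, %AUCexp is listed per subject, and a mis-scaled filter would probably be noticed. That is fair, and 20% is the likely meaning. But r² is a decimal on its own 0-to-1 scale, whereas %AUCexp is expressly a percentage. Noticing the problem after the concentrations are known would make the correction a post hoc choice.

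**The associated parameters can be inferred, and protocol 10.4.2 leaves analysis detail to the SAP.** This largely stands for CL and Vz, and whether SAP Section 11 must record the extension is arguable. The status of t1/2 remains unstated.

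**The missing days are clerical.** Also largely right. The samples are drawn under the protocol, SAP 8.3 uses actual sampling times, and SAP 8.1 excludes only missing values and certain values connected with BLQ results. No text tells the analyst to discard a collected sample, so the Step 3 error is conditional. Part of it is trapezoid bias present on the full schedule, and if half-life is similar across doses it acts as a near-constant multiplier that leaves the dose-proportionality slope almost unchanged.

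**The counts mostly restate the assumed half-life, and they suppose quantifiable data to Day 120.** True. At 7 days that supposes a 2^17, about 131,000-fold, fall; at 10 days about 3,800-fold. With earlier BLQ, retention at 0.2% depends on the peak relative to an assay limit that the documents do not give. The counts of 30 and 26 are therefore best cases. The threshold arithmetic in Step 1 is the firm part.

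**Conclusion.** The concern holds. In both documents the cut-off is on a different scale from the parameter it limits, and followed as written it is one hundred times stricter than the probable intent: 9.0 half-lives of quantifiable decline against 2.3. If the half-life is well below 13 days and the assay follows the decline far enough, the two readings give nearly the same tables. From about 14 to 50 days, the unit decides whether AUC0-inf, and CL and Vz if they are the associated parameters, reach the summaries, and whether AUC0-inf reaches its dose-proportionality fit. These half-life limits assume a mono-exponential decline quantifiable to Day 120; the subject counts also rest on an assumed half-life and CV.

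The omission of Days 43 and 57 is a plain contradiction within the SAP and with the protocol. Its direct effect is on concentration summaries and mean plots; the AUC effect arises only if the short list is used to select samples. Safety analyses are not involved, and Cmax, AUC0-48 and AUC0-tlast are unaffected by the cut-off. It should be corrected, but it does not threaten the primary objective.

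**What to change.** - In SAP 8.3 and protocol 10.4.3, state the limit as %AUCexp below 20%, or redefine the quantity as an extrapolated fraction with a limit of 0.20, after the sponsor confirms that this is what was meant.
- In SAP 8.3, name the parameters removed together with AUC0-inf (CL and Vz), and say whether t1/2 is governed only by the r² rule. Record the extension in SAP Section 11.
- Add Days 43 (±3) and 57 (±3) to the PK sampling list in SAP 8.2, and Days 43 and 57 to footnote q of SAP Appendix 1.
- Editorial: write Vz as Dose/(AUC0-inf × λz), so that a one-line reading does not multiply by λz.

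The cost is wording only. No sample or visit is added, since Days 43 and 57 are already drawn under the protocol. The unit should be settled before concentration data are available to the analysts.

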8.4. Pharmacokinetic Statistical Analysis

Dose-proportionality for AV-1 will be evaluated for C_{max} , AUC_{0-tlast}, and AUC_{0- ∞}. A power model will be fitted to describe the relationship between Y (C_{max} , AUC_{0-tlast} and AUC_{0- ∞}) and X (dose) using the least-squares linear regression model [ln(Y) = ln(β_0) + β_1 ln(X)].

From each model, the intercept of regression line $[\ln(\beta_0)]$ and the slope of the regression line β_1 will be presented along with the 90% confidence interval (CI) of the slope. Dose-proportionality will be concluded if the 90% CI of the slope β_1 lies entirely within $[1+\ln(0.8)/\ln(r), 1+\ln(1.25)/\ln(r)]$, where r is a ratio that describes the dose range and is defined as the ratio of highest dose/lowest dose. If dose proportionality is not observed, then the lowest dose followed by the highest dose in succession will be removed, and the model will be fit again after the removal of a dose until dose proportionality is achieved or less than 3 dose groups remain.

The statistical analyses will be based on the PK population.

9. Anti-AV-1 Antibody Analysis

Blood samples for immunogenicity analysis will be collected at Check-in (Day -1) and on Days 29 (±2), 85 (±5), and 120 (±5) (or ET). A validated ECL ELISA method will be used for detection and confirmation of preexisting and treatment-emergent anti-AV-1 antibodies in serum samples based on the MesoScale Discovery platform that utilizes labeled AV-1 for detection of anti-AV-1 antibodies and treatment emergent antibodies.

Frequency and percentage of subjects who show detectable anti-AV-1 antibody signal in serum, including treatment-emergent anti-AV- antibodies, will be summarized for the safety population. Pharmacokinetic parameters may be displayed based on anti-AV-1 antibody status as applicable.

Anti-AV-1 antibody data will be presented in a data listing for the safety population.

10. Safety Analysis

All safety summaries and analyses will be conducted for the safety population.

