3.2.2 Secondary

The secondary objectives of the study are the following:

- To characterize the PK of AV-1 following a single IV dose.
- To evaluate if subjects develop anti-AV-1 antibodies following a single IV dose of AV-1.

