3.3.2 Secondary Endpoints

The secondary endpoints of the study are the following:

- Single dose PK including area under the serum concentration-time curve (AUC) from time 0 to infinity (AUC_{0-∞}), AUC from time 0 to 48 hours postdose (AUC₀₋₄₈), AUC from time 0 to the time of the last quantifiable concentration (AUC_{0-tlast}), maximum observed serum concentration (C_{max}), time of the C_{max} (T_{max}), apparent serum terminal elimination half-life (t_{1/2}), total serum clearance (CL), and volume of distribution during the terminal phase (V_z) calculated from serum AV-1 levels measured using an electrochemiluminescence (ECL) enzyme-linked immunosorbent assay (ELISA).
- Incidence of anti-AV-1 antibodies as measured by the proportion of subjects with detectable anti-AV-1 antibody signal in serum, including treatment-emergent anti-AV-1 antibodies, using an ECL ELISA.

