7.2.3 Anti-AV-1 Antibody Sampling

Blood samples for anti-AV-1 antibody analysis will be collected at Check-in (Day -1) and on Days 29 (± 2), 85 (± 5), and 120 (± 5) (or ET). A validated ECL ELISA method will be used for detection and confirmation of pre-existing and treatment-emergent anti-AV-1 antibodies in

serum samples based on the MesoScale Discovery platform that utilizes labeled AV-1 for detection of anti-AV-1 antibodies and treatment-emergent antibodies.

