3.1. Overall Study Design and Plan

This is a Phase 1a, first-in-human, single-center, double-blind, randomized, placebo-controlled, sequential-group, single ascending dose study to determine the safety of AV-1 in healthy male and female adult subjects when administered as a single IV infusion. Additionally, the PK and the incidence of anti-AV-1 antibody responses will be studied.

Five sequential cohorts of 8 subjects (6 active and 2 placebo) each (Cohorts 1 to 5) are planned for this study. The starting dose of AV-1 will be 30 mg:

The study will consist of a screening period, check-in, a treatment period, and 8 follow-up visits for each cohort.

Potential subjects will be screened to assess their eligibility to enter the study within 35 days prior to investigational product (IP) administration. Eligible subjects will check in to the clinical site on Day -1 (the day before dosing). In each cohort, subjects will fast overnight (nothing to eat or drink except water) for at least 10 hours before the start of the IP infusion. Subjects will remain fasted for 4 hours after dosing with the IP. Subjects will be randomly assigned to receive AV-1 or placebo as follows:

- Cohort 1: AV-1 30 mg (n = 6) or placebo (n = 2) administered as an IV dose
- Cohort 2: AV-1 90 mg (n = 6) or placebo (n = 2) administered as an IV dose
- Cohort 3: AV-1 250 mg (n = 6) or placebo (n = 2) administered as an IV dose
- Cohort 4: AV-1 500 mg (n = 6) or placebo (n = 2) administered as an IV dose
- Cohort 5: AV-1 1000 mg (n = 6) or placebo (n = 2) administered as an IV dose

Sentinel dosing will be used in each cohort as discussed in Protocol Section 8.2.3. In each cohort, the Investigator will review safety data for the sentinel subjects and notify the Sponsor of intent to proceed with dosing the rest of the cohort with a minimum of 72 hours between dosing of the sentinel subjects and dosing the rest of the cohort. Safety data through Day 8 will be reviewed in a blinded fashion by the Safety Review Committee for each dose cohort before escalating to the next dose cohort. Based on the review of safety data, the Sponsor and the Investigator may choose to repeat a dose level, administer a dose less than the previous dose, escalate to a dose lower than the next planned dose, or prolong the duration of the infusion.

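### SAP 9 has no rule for antibody samples in which no signal is detected while AV-1 is still in the serum, so anti-AV-1 incidence may be understated, with greater risk at the higher doses

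*SAP*

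**What the plan says.** Protocol 3.2.2 sets the secondary objective: "To evaluate if subjects develop anti-AV-1 antibodies following a single IV dose of AV-1". Protocol 3.3.2 turns it into an endpoint: "Incidence of anti-AV-1 antibodies as measured by the proportion of subjects with detectable anti-AV-1 antibody signal in serum". SAP 3.2.3 repeats that definition.

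SAP 9 describes sampling and assay. "Blood samples for immunogenicity analysis will be collected at Check-in (Day -1) and on Days 29", 85 and 120 (or early termination), in every cohort. "A validated ECL ELISA method will be used for detection and confirmation of preexisting and treatment-emergent anti-AV-1 antibodies", and the platform "utilizes labeled AV-1 for detection of anti-AV-1 antibodies and treatment emergent antibodies"; Protocol 7.2.3 says the same. The planned summary is the "Frequency and percentage of subjects who show detectable anti-AV-1 antibody signal in serum", in the safety population, which SAP 4.2 defines to include placebo subjects. SAP 9 names no grouping; the default in SAP 4 for outputs summarized by treatment is each dose level, with placebo pooled.

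The AV-1 concentration is measured at the same visits: SAP 8.2 and Protocol 7.2.2 list PK samples on Days 29, 85 and 120 (or early termination). The only link SAP 9 makes between the two data sets is an optional display of PK parameters by antibody status.

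Neither document gives a drug-tolerance limit, a step that frees drug-bound antibody, an inconclusive category, or an explicit denominator for the percentage.

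**The concern.** An assay that finds antibody by its binding to labeled AV-1 can be blocked by unlabeled AV-1 in the same sample, which offers the same binding sites. A subject who has made antibody may then show no signal until enough drug has cleared. The planned percentage has two outcomes, detected or not, so such a subject stays in the denominator and out of the numerator. The sample is not missing. It is present but may not be interpretable.

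Sampling days do not depend on dose, so on any given day the higher cohorts can be expected to carry more residual drug. If masking occurs, it would be most frequent there, and a falling antibody rate with dose could be an artefact of fixed sampling days. An early-termination sample could be drawn sooner, at a higher drug level, and would be read the same way. The optional PK display would place any masked positive in the antibody-negative group. Protocol 2.2.1 says the study is meant to guide further development, so these rates are likely to be read.

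**Working it through.** **Inputs from the documents.** Doses are 30, 90, 250, 500 and 1000 mg, with six AV-1 and two placebo subjects per cohort (SAP 3.1). Post-dose antibody samples are on Days 29, 85 and 120, which are 28, 84 and 119 days after dosing. AV-1 has no prior human data (Protocol 2.2.1).

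**The plan's own figure.** The only stated number bearing on the denominator is the sample size: 5 × (6 + 2) = 40, that is 30 AV-1 and 10 placebo subjects. It reproduces. No antibody incidence, tolerance limit or residual AV-1 level is given.

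**Dose ratio.** 1000/30 = 33.3. This is a ratio of doses. It is also the ratio of residual AV-1 only if exposure is dose proportional and the half-life is the same in all cohorts.

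**How long the gap lasts.** Under those two assumptions and mono-exponential decline, 1000 mg needs log2(33.3) = 5.06 more half-lives than 30 mg to reach the same level. Day 29 to Day 120 is 119 − 28 = 91 days. The last 1000 mg sample then holds more drug than the first 30 mg sample if the half-life exceeds 91/5.06 = 18.0 days, whatever the volume. For 500 mg the crossover is 91/log2(500/30) = 91/4.06 = 22.4 days.

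**Illustrative levels.** C = (Dose/V) × 2^(−(Day − 1)/t½). Half-life and volume are assumptions; here V = 5 L. Values are in µg/mL.

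| Assumed t½ (days) | 1000 mg, Day 29 | 1000 mg, Day 85 | 1000 mg, Day 120 | 30 mg, Day 29 | 30 mg, Day 120 |
|---|---|---|---|---|---|
| 14 | 50 | 3.1 | 0.6 | 1.5 | 0.02 |
| 21 | 79 | 12.5 | 3.9 | 2.4 | 0.12 |
| 28 | 100 | 25 | 10.5 | 3.0 | 0.32 |

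With half-lives of 7 to 28 days and volumes of 3 to 6 L, the 1000 mg level runs from 10 to 167 at Day 29 and from 0.001 to 18 at Day 120.

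**If half-lives differ between cohorts.** The ratio of 1000 mg to 30 mg becomes 33.3 × 2^((Day − 1)/t½,low − (Day − 1)/t½,high). With 21 days at the low dose and 14 at the high dose it is 21 at Day 29 and 4.7 at Day 120. With 14 and 21 days it is 53 and 238.

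**What masking would do, if it happened.** Assume a true incidence of 20% at every dose, with a share m of positives masked in the 500 and 1000 mg cohorts only (12 of 30 AV-1 subjects). Those two cohorts report 20% × (1 − m), and all AV-1 subjects together report [18 × 0.20 + 12 × 0.20 × (1 − m)]/30.
- m = 0: 20% and 20%, no bias.
- m = 0.5: 10% and 4.8/30 = 16%.
- m = 1: 0% and 3.6/30 = 12%.

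The documents do not say which m applies.

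**Choice of denominator.** Suppose all six 1000 mg subjects stay above the limit at every visit and one reads positive. Dropping the five inconclusive subjects but keeping the positive gives 1/1 = 100%. Keeping all six gives 1/6 = 17% if the inconclusive subjects are taken as negative and 6/6 = 100% if taken as positive. Only the second presentation shows how little is known.

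**The case against.** The strongest reply is that nothing in the documents shows interference. The method is described as validated, with both detection and confirmation. If its tolerance covers the levels present, every undetected result is a true negative and the planned percentage is right. This stands. A reader might infer from the assay format and the dose range that incidence is understated at 500 and 1000 mg, or that residual AV-1 differs 33-fold between cohorts. The documents support neither: 33-fold is the dose ratio, and both residual drug and tolerance are unknown. Nor does the SAP say that an undetected signal is negative; that follows from how a two-outcome percentage is built.

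Late sampling also helps. In the 14-day example, 1000 mg falls about 90-fold between Days 29 and 120 and ends below the Day 29 level of 30 mg, so a persistent response masked early could be found later. That protection weakens with a longer half-life, a short-lived response or early termination.

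The consequences are limited. Protocol 10.1 plans no formal hypothesis test, and SAP 9 plans no comparison of incidence across doses. With six subjects, 0/6 has an exact 95% interval of 0 to 45.9%, so a zero cannot show low immunogenicity in any case. The listings would let a careful reader match antibody results to concentrations. These points keep the matter modest, but do not remove the gap: the summary would show 0/6 for a cohort in which no sample could be interpreted and for one with six clear negatives.

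**Conclusion.** The gap is real; its effect is conditional. SAP 9 does not separate an undetected result in a sample that still contains interfering AV-1 from one in a sample that does not, although the concentration needed to do so is measured at the same visits. Incidence may be understated, with greater risk at the higher doses. That rests on two conditions: that AV-1 in some samples exceeds what the assay tolerates, and that residual drug rises with dose. The first cannot be checked from the documents. The second is likely, but its size is unknown in a first-in-human study.

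The bias cannot be computed. The assumed 20% example spans no effect to 0% reported in the top two cohorts, and 20% down to 12% across all AV-1 subjects. This is an inexpensive improvement to a secondary summary, not a demonstrated error in a result.

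**What to change.** In SAP 9:
1. State the validated drug-tolerance limit of the antibody assay.
2. Compare it with the AV-1 concentration at the same visit. Class an undetected post-dose result above the limit as inconclusive, and one at or below the limit as negative. A detected and confirmed signal is positive at any concentration.
3. Report positive, negative and inconclusive counts by dose group, with placebo separate, and by visit. State how visit results combine into one result per subject.
4. Keep all dosed subjects with a post-dose sample in the primary denominator. Show incidence as a range, with inconclusive subjects taken as all negative and as all positive. Do not use a denominator that keeps positives at any drug level but drops inconclusive subjects, because inclusion would then depend on the outcome.
5. In any PK display by antibody status, keep inconclusive subjects out of the antibody-negative group.

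The cost is SAP wording and an extra table column. No new samples are needed, and if the assay tolerates the levels present, no result changes class. The downside is that some high-dose results will be reported as inconclusive, and the range for a small cohort may be wide.
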